### **7.5. Mid-Parental Height Assessment**

The calculation of mid-parental height has been a standard procedure for assessing individual child's future adult height since it was first described by Tanner {Tanner 1970}. Mid-parental height will be calculated as the average of father's and mother's height. For boys, the sex-adjusted mid-parental height will be calculated by adding 2.5 inch or 6.5 cm from the mean of the parents' heights. For girls, will be calculated by subtracting 2.5 inch or 6.5 cm from the mean of the parents' heights. If any one of parents' heights is missing, the calculation will be excluded.

A by-subject listing of parents' heights and derived mid-parental height will be provided by subject ID number in ascending order.

### **7.6. Bone Age Assessment**

Bone age at baseline visit, FU-24 visit and change from baseline visit will be summarized for the Safety Analysis Set in each age group using descriptive statistics (n, mean, SD, median, Q1, Q3, minimum, and maximum).

A by-subject listing of bone age will be provided by subject ID number in ascending order and visit in chronological order.

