2. OBJECTIVES

The primary objective of the PK Lead-in phase is:

- To evaluate the steady state pharmacokinetics (PK) and confirm the dose of sofosbuvir/velpatasvir (SOF/VEL FDC) in pediatric subjects with chronic hepatitis C virus (HCV) infection

The primary objective of the Treatment Phase of this study is:

- To evaluate the safety and tolerability of SOF/VEL FDC for 12 weeks in pediatric subjects with chronic HCV

[figure not shown]
The secondary objective of the PK Lead-in Phase is:

- To evaluate the safety, tolerability, and antiviral activity of 7 days of dosing of SOF/VEL FDC in pediatric subjects with chronic HCV

The secondary objectives of the Treatment Phase of this study are:

- To determine the efficacy of SOF/VEL FDC for 12 weeks in pediatric subjects with chronic HCV infection, as assessed by the proportion of subjects with sustained virological response (SVR) 12 weeks after cessation of treatment (SVR12)
- To determine the proportion of subjects with SVR 4 and 24 weeks after cessation of treatment (SVR4 and SVR24)
- To evaluate the proportion of subjects with virologic failure, including breakthrough/nonresponse and relapse
- To evaluate the kinetics of circulating HCV RNA during treatment and after cessation of treatment
- To evaluate the emergence of viral resistance to SOF and VEL during treatment and after cessation of treatment
- To evaluate the effect of treatment with SOF/VEL FDC on quality of life as measured by PedsQL™ Pediatric Quality of Life survey
- To evaluate the effect of SOF/VEL FDC on growth and development of pediatric subjects during and after treatment
- To evaluate the acceptability, including palatability, of formulations used in the study

The exploratory objective of this study is:

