6.10.6. Bone Age Assessment

A single X-ray of the left wrist, hand, and fingers will be performed at Day 1 Visit and posttreatment Week 24. Local radiologist will determine bone age from x-ray.

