8.5.4.3. Bone Age Assessment

Bone age will be summarized.

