### **1.2.3. Study Duration**

The total time to complete all study visits is up to approximately 40 weeks including the following periods:

- 28-day (4-week) screening period
- 12-week treatment period
- 24-week posttreatment period

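### Bone age is summarised as raw change over about 36 weeks with no reference to chronological age, so the mean change cannot by itself separate normal from slowed or accelerated maturation

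*SAP*

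**What the plan says.** Protocol section 2 makes growth a secondary objective of the Treatment Phase: "To evaluate the effect of SOF/VEL FDC on growth and development of pediatric subjects during and after treatment". Protocol 3.1 names bone age among the measures for it, beside height and weight percentiles, Tanner stage and parental height.

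Protocol 6.10.6 sets the timing: "A single X-ray of the left wrist, hand, and fingers will be performed at Day 1 Visit and posttreatment Week 24". The same section names the reader: "Local radiologist will determine bone age from x-ray". It mentions no central reading and no reading standard.

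On analysis, Protocol 8.5.4.3 says only "Bone age will be summarized". SAP 7.6 adds the statistic: "Bone age at baseline visit, FU-24 visit and change from baseline visit will be summarized for the Safety Analysis Set", by age group, using the usual descriptive statistics, plus a by-subject listing.

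No other section supplies an age reference. SAP 3.3 rules out covariates, SAP 3.6 takes age at first dose for analyses, and SAP 5.2 lists baseline bone age in years as a characteristic of its own. By contrast, SAP 7.4 converts each weight, height and BMI value to a percentile for age and sex.

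**The concern.** Bone age is an age. In a growing child it is expected to rise by roughly the time that passes between two readings, so its raw change mixes elapsed time with any effect on the pace of maturation. There is no comparator arm to remove the first part. Chronological age is the natural internal reference, and the plan does not use it.

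Two misreadings are possible. A positive mean change could be taken as a drug effect or as reassurance when it is only the passage of time. A real slowing would also appear as a positive mean change, only a smaller one, with no stated value to compare it with. Protocol 1.1 describes concern about growth under the older interferon and ribavirin regimens, so this is a question readers will bring to the results.

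**Working it through.** **Inputs.** SAP 1.2.3 gives a 4-week screening period, a "12-week treatment period" and a "24-week posttreatment period". Visit windows are in Protocol 6.4.3 (Week 12, ±3 days) and 6.5.3 (posttreatment Week 24, +5 days). The documents give no expected change, SD or reading error for bone age, so such values below are marked as assumed.

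**Reproducing the plan's figure.** 4 + 12 + 24 = 40 weeks, which matches the total in SAP 1.2.3.

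**Interval between X-rays.**
- Nominal: 12 + 24 = 36 weeks; 36 × 7 = 252 days; 252 / 365.25 = 0.69 year.
- Shortest within visit windows: 84 − 3 + 168 = 249 days, 0.68 year.
- Longest within visit windows: 84 + 3 + 168 + 5 = 260 days, 0.71 year.
- Stops at Week 4 and attends posttreatment Week 24: 28 + 168 = 196 days, 0.54 year.

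**Expected mean change.** Let r be bone-age years gained per calendar year (assumed; r = 1 is normal pace). Raw change = r × 0.69. Change minus elapsed time = (r − 1) × 0.69.

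| r | Raw change (years) | Change minus elapsed time (years) |
|---|---|---|
| 0.5 | +0.34 | −0.34 |
| 0.75 | +0.52 | −0.17 |
| 1 | +0.69 | 0.00 |
| 1.25 | +0.86 | +0.17 |
| 1.5 | +1.03 | +0.34 |

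The raw mean is positive in every row. Only the last column shows the direction of a departure.

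**Individual children.** With normal maturation and change taken as normally distributed with mean 0.69 and an assumed SD of 0.6 to 1.0 year, the share showing no increase is Φ(−0.69/SD), about 12% to 25%. Starting instead from an assumed error SD per reading of 0.25, 0.5, 0.75 or 1.0 year (SD of the change = √2 times that), the shares are 2.6%, 16.5%, 25.8% and 31.3%.

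**Skeletally mature subjects.** A mature subject contributes 0 − 0.69 = −0.69 year to the corrected change. If 10% to 30% of the 12 to <18 group were mature (assumed), the corrected mean would be 0.10 × (−0.69) = −0.07 to 0.30 × (−0.69) = −0.21 year with no drug effect.

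**Precision.** SE = SD/√n. For an assumed SD of 0.6 to 1.0 year, SE is 0.06 to 0.10 at n = 100 and 0.15 to 0.24 at n = 17, the Cohort 3 minimum.

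**Birth-date imputation.** For one child, (bone age₂ − age₂) − (bone age₁ − age₁) = (bone age₂ − bone age₁) − (date₂ − date₁). The birth date cancels. The 01 July rule in SAP 3.6 can therefore shift bone age minus age by up to about half a year, but it leaves change minus elapsed time untouched.

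**The case against.** The sponsor has a fair reply on several counts.

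- *Readers can subtract 0.69 themselves.* For the group mean among completers this nearly works, since the interval runs only from 249 to 260 days, and mean age and mean bone age at baseline are both tabulated. It fails for early discontinuers, whose interval can be far shorter. It also cannot recover how bone age minus age varies between children, because that spread does not follow from two separate group summaries.
- *The correction can create its own signal.* This stands. It assumes one bone-age year per calendar year, which the documents do not state, and enrolment runs up to <18 years. Mature adolescents would pull the corrected mean below zero, so the correction needs a caveat and a second display.
- *The SAP is descriptive.* This also stands as far as a confidence interval goes: SAP 7.4 excludes inferential statistics for weight and height. The added summaries can be purely descriptive.

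A reader might also infer two stronger things. One is that every child will show an increase. Reading error and completed maturation can produce zero or negative changes, so only a positive mean is expected. The other is that the growth objective goes unanswered. It does not: SAP 7.4 gives age- and sex-specific percentiles with change from baseline, SAP 7.7 tabulates Tanner stage by baseline stage and sex, and Protocol 3.10 places longer-term growth in a separate 5-year registry study.

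**Conclusion.** The point holds for the bone-age component only. About +0.69 year of mean change is expected with no drug effect, and maturation at half pace would still give about +0.34 year, so the sign of the planned statistic says nothing about slowing and its size has no stated reference. The interval comes from the documents; the expected gain assumes normal maturation of one bone-age year per calendar year in subjects still growing.

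How well a departure could be seen depends on group size and on an SD the documents do not give. A 0.34-year shortfall is several standard errors at n = 100 under the assumed SDs, but only about 1.4 to 2.3 at n = 17 (0.34/0.24 and 0.34/0.15), so the n = 100 figure should not be carried over to the 3 to <6 group. The interpretive problem itself does not depend on n.

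This is a low-cost improvement to one secondary endpoint. The primary safety endpoint and SVR12 are unaffected.

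**What to change.** In SAP 7.6, keep the raw values and the listing, and add descriptive summaries by age group of:

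- (a) bone age minus chronological age at the date of each X-ray, using age on that date and not the age at first dose fixed in SAP 3.6;
- (b) change in bone age minus elapsed time between the two X-rays, both in years.

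Define in advance how a subject is classed as skeletally mature at baseline, flag those subjects, and present (b) with and without them. Add a note that the 01 July birth-date rule affects (a) but not (b). A 95% CI for (b) is optional; any statement about precision should be given by actual group size and marked as resting on an assumed SD.

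The cost is two derived variables, one flag and a few lines of SAP text. No new assessment is needed. X-ray dates should already be recorded, although the documents do not show the eCRF. The small downside is the extra derivation and the caveat that mature adolescents require.

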### **7.7. Tanner Pubertal Stage Assessment**

The Tanner stages will be used to evaluate the onset and progression of pubertal changes. Females will be rated for pubic hair growth and breast development, and males will be rated for pubic hair growth and genitalia development. If the subject is at a Tanner 5 at Day 1, no further Tanner Pubertal Stage Assessments are to be completed. The Tanner stages (Pubic Hair and Breasts for female; Pubic Hair and Genitalia for male) at EOT, FU-12 and FU-24 visit will be summarized by baseline Tanner stages using frequency count and percentage by sex for each age group.

Tanner stage results at baseline and during the study will be listed.

### **7.8. Prior and Concomitant Medications**

Medications collected at screening and during the study will be coded using the current version of the World Health Organization (WHO) Drug dictionary. The medications will be categorized as prior or concomitant using the following definitions:

- Prior medications: any medications taken and stopped prior to or on the date of first study drug administration
- Concomitant medications: any medications taken after the date of first study drug administration and up to the last dosing date of study drug

Concomitant medications will be summarized by preferred name using the number and percentage of subjects for the Safety Analysis Set in each age group. A subject reporting the same medication more than once will be counted only once when calculating the number and percentage of subjects who received that medication. The summary of concomitant medications will be ordered by preferred term in descending frequency. For drugs with the same frequency, sorting will be done alphabetically.

Summaries will be based on the Safety Analysis Set. No inferential statistics will be generated.

For purposes of analysis, any medication with a stop date that is on or prior to the initial study drug dosing date or a start date that is after the last study drug dosing date will be excluded from a concomitant medication summary. If a partial stop date is entered, any medication with the month and year (if day is missing) or year (if day and month are missing) prior to the initial study drug dosing date will be excluded from the concomitant medication summary. If a partial start date is entered, then any medication with the month and year (if day is missing) or year (if day and month are missing) after the study drug stop date will be excluded from the concomitant medication summary. Medications with completely missing dates will be included in the concomitant medication summary.

A summary of prior medications will not be provided.

All prior and concomitant medications (other than per-protocol study drugs) will be provided in a by-subject listing sorted by subject ID number and administration date in chronological order.

#### **7.9. Swallowability Assessment for SOF/VEL FDC Placebo Tablets**

[figure not shown]
For subjects in the 12 to <18 and 6 to <12 years of age groups, swallowability of SOF/VEL FDC placebo tablets will be summarized using the numbers and percentages of subjects in each swallowability category (ie, Able to Swallow, Unable to Swallow).

A by-subject listing of Swallowability of SOF/VEL FDC placebo tablets will be provided by subject ID number in ascending order.

#### **7.10. Acceptability and Palatability of SOF/VEL FDC**

A questionnaire will be administered to subjects to assess acceptability and palatability of the formulation they received on Day 1, Week 12 and Early Termination (as applicable). If the subject is unable to complete the questionnaires, the parent/legal guardian will assist to complete the questionnaire on their behalf. The subject's parent/legal guardian will also complete a questionnaire on Week 12 or Early Termination (as applicable) for their assessment of acceptability of the formulation the subject received.

Acceptability and palatability will be assessed by numeric response marked on line between numbers 0-100 (higher scores indicate better acceptability and/or palatability) in response to questions about how the study drug tasted, how easy it was to swallow the study drug, and, for those who received that tablet formulation, how they felt about the number of tablets they had to swallow.

Responses to the acceptability and palatability questionnaire by subjects and their parent/legal guardian at Day 1, Week 12 and Early Termination (as applicable) will be respectively summarized by formulation (ie, SOF/VEL FDC400/100 mg adult tablet, 200/50 mg low dose tablets and oral granules) and by dose (SOF/VEL 400/100 mg tablet, SOF/VEL 200/50 mg, SOF/VEL 150/37.5 mg) for each age group using the numbers and percentages of subjects in the following categories, as applicable:

- Did not taste the study drug (for question regarding study drug taste only)
- Score marked > 60 to 100
- Score marked 40 to 60
- Score marked 0 to < 40

A by-subject listing of acceptability and palatability of SOF/VEL FDC will be provided by subject ID number in ascending order.

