Criteria for Evaluation:

- Safety:** AEs, laboratory tests, physical examinations, and vital sign measurements will be collected throughout the study.
- Efficacy:** Efficacy will be evaluated using scheduled assessments of HCV RNA performed using COBAS[®] AmpliPrep/COBAS[®] TaqMan[®] HCV test.
- Pharmacokinetics:** For subjects in the PK Lead-in, the steady-state PK of VEL, SOF, and its major metabolite (GS-331007) will be assessed at Day 7. Plasma PK parameters such as C_{max} , T_{max} , C_{last} , T_{last} , C_{tau} , AUC_{tau} , CL/F , Vz/F and $t_{1/2}$ will be estimated, as appropriate.
- Intensive PK and safety results from the PK Lead-in Phase of each cohort will be reviewed to confirm the appropriateness of the evaluated SOF/VEL FDC dose for the Treatment Phase in that age group.
- For all subjects in the Treatment Phase, sparse PK blood samples will be collected at all visits while on treatment. The PK of SOF, its primary metabolite GS-331007, and VEL will be assessed.

Statistical Methods: For the PK Lead-in, the primary plasma PK parameters are AUC_{tau} , for SOF, GS-331007, and VEL. All PK parameters will be summarized by cohort. The effect of age and SOF/VEL FDC dose on PK will be explored.

For the Treatment Phase, the primary safety endpoint is review of any AEs with a focus on AEs that lead to discontinuation of study drug. The key efficacy endpoint is SVR12 in all enrolled and treated subjects. The point estimate of the SVR12 rate and the 2-sided 95% exact confidence interval based on the Clopper-Pearson method will be provided. The secondary efficacy endpoints include SVR4 and SVR24.

Clinically relevant subgroup analyses on SVR12 may be conducted as appropriate (ie, assuming that adequate numbers of patients in these subsets are available for analysis).

All continuous endpoints will be summarized using an 8-number summary (n, mean, standard deviation, median, Q1, Q3, minimum, and maximum). All categorical endpoints will be summarized by number and percentage of subjects who meet the endpoint definition.

Safety endpoints will be analyzed by the number and percent of subjects with events or abnormalities for categorical values or by the 8-number summary (n, mean, standard deviation, median, Q1, Q3, minimum, maximum) for continuous data.

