5.2. Dosage and Administration of SOF/VEL FDC

Subjects 12 to < 18 years old enrolled in the PK Lead-in Cohort 1 or in the Treatment Phase

SOF/VEL FDC 400/100 mg tablets will be administered once daily with or without food. Subjects determined unable to swallow the placebo to match the 400/100 mg SOF/VEL FDC tablet will be re-assigned to 2 x 200/50 mg SOF/VEL FDC tablets daily. Subjects unable to swallow the reduced strength SOF/VEL FDC 200/50 mg tablets will be reassigned to SOF/VEL FDC oral granule formulation (8 x 50/12.5 mg packets).

Subjects 6 to < 12 years old enrolled in the PK Lead-in Cohort 2 or in the Treatment Phase

SOF/VEL FDC 200/50 mg tablets will be administered once daily with or without food. Subjects determined unable to swallow the placebo tablet 200/50 mg SOF/VEL FDC will be reassigned to SOF/VEL FDC oral granule formulation (4 x 50/12.5 mg packets).

Subjects 3 to < 6 years old enrolled in the PK Lead-in Cohort 3 or in the Treatment Phase

SOF/VEL FDC 50/12.5 mg oral granules in a packet will be administered once daily with or without food. Subjects who weigh ≥ 17 kgs will be assigned to 200/50 mg SOF/VEL FDC oral granules (4 x 50/12.5 mg packets) and subjects who weigh < 17 kgs will be assigned to 150/37.5 mg SOF/VEL FDC oral granules (3 x 50/12.5 mg packets). The instructions dosing of oral granules are defined in Section 5.2.1.

Subjects should be instructed that if vomiting occurs within 3 hours of dosing an additional tablet or granules packets should be taken according to the dosing instructions above. If vomiting occurs more than 3 hours after dosing, no replacement dose is required that day.

If a dose is missed and it is within 18 hours of the normal regular scheduled time, subjects should be instructed to take the tablet or granules as soon as possible and then follow with the next dose at the usual scheduled time.

If it is after 18 hours then it is considered a missed dose. Subjects should be instructed to take the next dose at the usual next scheduled time. Subjects should be instructed not to take a double dose.

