#### **7.12. Changes From Protocol-Specified Safety Analyses**

There are no deviations from the protocol-specified safety analyses.

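### SAP 7.10 tabulates the 0-100 acceptability and palatability scores only in three bands, without the 8-number summary set for continuous endpoints, and its by-dose labels do not clearly cover every 400/100 mg regimen

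*SAP*

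**What the plan says.** Acceptability, including palatability, is a secondary objective of the Treatment Phase (Protocol section 2) and a listed secondary endpoint (Protocol 8.1.3).

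- **Measurement.** SAP 7.10: "Acceptability and palatability will be assessed by numeric response marked on line between numbers 0-100". Higher scores are better. The questions cover taste, ease of swallowing and, for tablet users, the number of tablets.
- **Tabulation.** The responses are summarized "using the numbers and percentages of subjects in the following categories, as applicable". The categories are the three score bands, plus a did-not-taste response for the taste question. SAP 7.10 plans no mean, median, measure of spread or change score. It does keep individual data: "A by-subject listing of acceptability and palatability of SOF/VEL FDC will be provided by subject ID number in ascending order".
- **General rules.** Protocol synopsis, Statistical Methods: "All continuous endpoints will be summarized using an 8-number summary (n, mean, standard deviation, median, Q1, Q3, minimum, and maximum". SAP section 3 lists nearly the same statistics for continuous variables.
- **Declared changes.** SAP 7.12: "There are no deviations from the protocol-specified safety analyses".
- **Rows.** SAP 7.10 summarizes by formulation (adult tablet, low dose tablets, oral granules) and "by dose (SOF/VEL 400/100 mg tablet, SOF/VEL 200/50 mg, SOF/VEL 150/37.5 mg"), for each age group. In the 12 to <18 group, Protocol 5.2 starts with the 400/100 mg tablet, moves those unable to swallow it to two 200/50 mg tablets, and has those who cannot swallow these "reassigned to SOF/VEL FDC oral granule formulation (8 x 50/12.5 mg packets").

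**The concern.** A score on a 0-100 line is continuous by any ordinary reading, and both documents say how continuous data are to be summarized. SAP 7.10 does something else and does not say so.

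Band counts cannot give a typical score or its spread. They also handle change badly. A child who moves from 62 to 98 between Day 1 and Week 12 shows no change, while one who moves from 59 to 61 changes band. Formulations that differ inside one band look the same.

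The dose labels raise a smaller, separate question. A programmer given SAP 7.10 has no by-dose label for an adolescent on 400/100 mg granules, and no instruction on where an adolescent on two 200/50 mg tablets belongs. One questionnaire item asks about the number of tablets, so one tablet versus two is a distinction the instrument is meant to capture.

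**Working it through.** **1. What band percentages say about the mean.** The bands run from 0 to 40, 40 to 60 and 60 to 100. The lowest possible mean is the sum of (share × lower edge); the highest is the sum of (share × upper edge).

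| Low / middle / high share | Lowest mean | Highest mean |
|---|---|---|
| 0 / 0 / 100% | 60 | 100 |
| 10 / 10 / 80% | 0 + 4 + 48 = 52 | 4 + 6 + 80 = 90 |
| 20 / 20 / 60% | 0 + 8 + 36 = 44 | 8 + 12 + 60 = 80 |

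This step needs no assumption about the distribution.

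**2. Share of score variance kept by the bands.** This is between-band variance divided by total variance. For a uniform score the band means are 20, 50 and 80 with shares 0.4, 0.2 and 0.4. Between-band variance is 0.8 × 30² = 720, total variance is 100²/12 = 833.3, and the ratio is 0.86. The documents give no score distribution, so the shapes below are assumptions.

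| Assumed shape on 0-100 | Mean | Share in top band | Variance kept |
|---|---|---|---|
| Uniform | 50 | 40% | 86% |
| Beta(3,2) | 60 | 53% | 82% |
| Beta(2,1) | 67 | 64% | 81% |
| Beta(3,1) | 75 | 78% | 72% |
| Beta(5,1) | 83 | 92% | 49% |
| Beta(8,2) | 80 | 93% | 40% |
| Beta(12,2) | 86 | 99% | 15% |

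**3. A second measure: information on the mean.** Assume a normal score cut at 40 and 60. With z = (cut − mean)/SD, relative Fisher information is the sum over bands of (difference in normal density at the band's edges)² / (band probability).

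| Mean | SD 15 | SD 20 | SD 25 |
|---|---|---|---|
| 70 | 0.57 | 0.64 | 0.67 |
| 80 | 0.33 | 0.46 | 0.53 |

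The normal model fits a bounded line poorly. With mean 80 it puts 9%, 16% and 21% of scores above 100 at SD 15, 20 and 25. Steps 2 and 3 agree on direction: the loss is moderate for spread-out scores and large when scores pile up at the top.

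**4. Regimens against rows.** 8 × 50/12.5 = 400/100 mg and 2 × 200/50 = 400/100 mg, which reproduces the 400/100 mg that Protocol 3.3.1 states for eight packets.

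| 12 to <18 regimen | By-dose label | By-formulation row |
|---|---|---|
| 1 × 400/100 mg tablet | 400/100 mg tablet | adult tablet |
| 2 × 200/50 mg tablets | unclear | low dose tablets |
| 8 packets | none | oral granules |

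The eight-packet entry follows Protocol 3.3.1 and 5.2. The synopsis also prints a four-packet line under the 12 to <18 heading, and these passages must be reconciled before rows are labelled.

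**The case against.** The case for leaving SAP 7.10 alone has real content.

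- **The SAP may have chosen a categorical endpoint.** The protocol speaks of a questionnaire, never of a 0-100 score, and names no statistic for it. The 8-number rule is a general synopsis sentence followed by a rule for categorical endpoints. The did-not-taste response cannot enter a mean. That last point stands, and the fix must handle it. The rest is weaker. The protocol defines no bands, the SAP itself calls the response numeric, and SAP section 3 binds the SAP whatever the synopsis intends. SAP 6.2.2 presents another 0-100 measure, the PedsQL, as scores and changes from baseline.
- **A reader might infer that the endpoint loses most of its information.** The documents do not support that. Four of the six normal scenarios keep more than half, spread-out or moderately skewed scores keep about 70-90% of the variance, and every distribution is assumed.
- **A reader might infer that the two-tablet and eight-packet adolescents drop out, or are filed at half their dose.** They do not drop out, because the same sentence plans formulation rows by age group. As a dose label, 400/100 mg tablet could include two 200/50 mg tablets. Filing under 200/50 mg is conjecture.
- **A reader might infer that the 400/100 mg row overstates acceptability.** That row is labelled as tablets, and nothing in the documents says that children moved to another formulation rate it lower.
- **Little depends on it.** The analysis is descriptive, the by-subject listing remains, and swallowability (SAP 7.9) is reported separately. This stands and limits the weight of the point.

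**Conclusion.** The point holds as a reporting gap in one descriptive secondary endpoint. SAP 7.10 omits the 8-number summary that the synopsis and SAP section 3 set for continuous data, and SAP 7.12 does not record the departure. What is certain is that the tables will not show level, spread or within-band change. The amount of information lost is not certain: under the assumed distributions it runs from about 14% of the variance (uniform scores) to about 85% (Beta(12,2)), and it passes half only when scores cluster high.

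The dose-label point is narrower. There is no by-dose label for 400/100 mg granules, and the place of two 200/50 mg tablets is unclear, but both groups remain visible by formulation and age group. Neither part touches sample size, error rates or the collected data.

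**What to change.** In SAP 7.10:

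1. Add the 8-number summary of each 0-100 score at Day 1, Week 12 and Early Termination, as applicable, among subjects giving a numeric score. Count did-not-taste responses separately and keep the three bands as supplementary.
2. Add the same summary of within-subject change for the subject questionnaire. Protocol 6.10.7 and the opening of SAP 7.10 place the parent or guardian questionnaire only at Week 12 or Early Termination, so it has no Day 1 value to change from.
3. Relabel the by-dose rows so that each regimen the protocol permits has one unambiguous row, after the granule lines in the synopsis and Protocol 5.2 have been reconciled.

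If the sponsor prefers bands alone, SAP 7.12 should say so and give the reason. The cost is one extra table shell and a few lines of SAP text; no new data are needed.
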